5.3.2. Recruitment

Adults age 18 to 55 years will be recruited from the villages in the Kombewa Health and Demographics Surveillance System (HDSS) consisting of half of Kisumu West and all of Seme Sub-Counties of Kisumu County, Kenya. Potential participants identified from within the HDSS will be approached in the community using a recruitment script by study staff delegated to carry out recruitment. Informed consent will be obtained in accordance with section 13.3. Language and illiteracy will not be impediments in the recruitment process, all briefings and explanations will be in the understandable language of the participant. It is expected that approximately 1240 adult volunteers will have to be screened to achieve the 619 subject enrolment number. HIV-infected participants will be allowed to participate in this trial, assuming they meet all eligibility criteria (less than stage 3 HIV and in the opinion of the PI they are healthy enough to participate). The study is not seeking to actively enroll HIV-positive individuals. However, given the fact that the study area has a high prevalence of HIV, it is expected that there will be HIV-positive individuals in the screening population. Therefore, the screening for HIV and staging will ensure that only healthy HIV-positive individuals are included in the study. The proportion of HIV-positive subjects enrolled in the trial is intended to reflect the same proportionate make-up of HIV-positives in the recruitment catchment areas, estimated to be approximately 15%. As such, we intend to cap HIV-positive enrollees at approximately 20-25% to avoid an over-representation by HIV-positive subjects. Final determination for enrolment of HIV-positive subjects will be determined by the Principal Investigator.

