Note: HIV screening will be obtained to identify subjects positive for HIV. Subjects found to be HIV positive will have a confirmatory laboratory test as per local standard of care procedures. A positive HIV test does NOT exclude the subject from participation in the trial by itself, though a cap on enrolment of HIV positive participants will be implemented as needed by the Principal Investigator, as discussed above. Subjects found to be HIV positive (stage 1 and 2) will be equally randomized among all study groups to the extent possible and within the limits of the cap. Subjects will be verbally consented for HIV testing according to the local standard of care. If a participant has been previously screened for this study and is being rescreened outside of the window, HIV-testing will only be repeated if it is >90 days from their initial negative screening HIV testing at the clinic. In this same scenario but where they initially screened HIV-positive at the clinic while screening for this study, they will not require any repeat HIV screening. In the cases where HIV screening will not be repeated, the prior HIV test result from their initial screening attempt will be transcribed to the CRF for their new screening ID.

B. Epoch 1 - The Treatment and Immunization Phase (Appendix B)

Appendix B shows the visit number, study day, window periods, and blood sampling volumes for all study procedures for Visits 2 to 18. When screening and review of inclusion/exclusion criteria are complete, a picture ID card of each eligible volunteer will be created using the stored photo. In addition to the subject's photo, subject ID number and the study number and name, the card will contain contact information for KCRC. Subjects will be assigned a subject ID number sequentially upon randomization; example: CVIA078-001. This will ensure that the subject can contact an investigator, and the clinic can be contacted if medical care is received outside the study health facilities. Copies of these pictures will

be kept in the subjects' records to aid the study staff in confirmation of the volunteers' identification for future visits. The photos of subjects who are determined ineligible to participate during screening will be deleted from the computer.

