10. STATISTICAL CONSIDERATIONS

10.1. Statistical Analysis Plan

The statistical analysis will be conducted following the principles as specified in the International Conference on Harmonization (ICH) Topic E9 (ICH, 1998). The final statistical analyses will be performed after database lock.

All data will be collected and verified prior to analysis. Detailed statistical procedures, listings, table shells, and figures will be provided in a statistical analysis plan (SAP) prior to analysis. The SAP will be finalized before study close-out and database lock. The following key statistical components and a detailed description will be documented in the SAP:

- Primary and secondary endpoints and how they will be measured
- Statistical methods and tests that will be used to analyze the endpoints
- Strategy that will be used if the statistical test assumptions are not satisfied
- Indication of whether the comparisons will be using one-tailed or two-tailed tests (with justification of the choice) and the level of significance to be used
- Identification of whether any adjustments to the significance level or the overall p value will be made to account for any planned or unplanned subgroup analyses or multiple testing
- Specification of potential adjusted analyses and a statement with which covariates or factors will be included
- Planned exploratory analyses and justification of their importance

The number of subjects enrolled, vaccinated, completed, or withdrawn will be summarized. Reasons for withdrawal, when known, will be provided. Demographic data will be summarized by descriptive statistics and will include total number of observations (n), mean, standard deviation (SD) and range for continuous variables, and number and percentages for dichotomous variables.

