10.4.2. Analysis of the Primary Efficacy Endpoint

Vaccine efficacy against the first PCR-positive *P. falciparum* infection among adults who were *P. falciparum* positive at baseline will be assessed using Cox proportional hazards regression with a covariate for group assignment to compare Groups 1 and 4. The vaccine efficacy estimates (1-hazard ratio), 95% CI, and p-values will be calculated from this model. Cumulative incidence graphs will also be provided. This analysis will be conducted in the ATP for efficacy cohort.

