10.4.3. Analysis of the Secondary Endpoint(s)

Efficacy:

Vaccine efficacy against the first PCR-positive *P. falciparum* infection among adults who were *P. falciparum* negative at baseline will be assessed using Cox proportional hazards regression with a covariate for group assignment to compare Groups 2 and 5. The vaccine efficacy estimates (1-hazard ratio), 95% CI, and p-values will be calculated from this model. Cumulative incidence graphs will also be provided. This analysis will be conducted in the ATP for efficacy cohort.

Immunogenicity:

The primary analysis will be based on the ATP for immunogenicity cohort for analysis of immunogenicity. A secondary analysis based on the TVC will be performed to complement the ATP analysis.

Anti-CS antibodies:

The percentage of subjects with sero-positive levels of anti-CS (proportion of subjects with anti-CS antibody levels with 95% CI) will be determined as shown in Appendix F. Antibody levels after the third dose will also be investigated using reverse cumulative curves.

Anti-HBs antibodies:

The percentage of subjects with sero-positive levels of anti-HBs (proportion of subjects with anti-HBs antibody levels greater than the lower limit of detection/assay dependent) will be determined prior to vaccination, and 14 days post Dose 3. Antibody levels after the third dose will also be investigated using reverse cumulative curves.

Anti-rabies antibodies:

The percentage of subjects in Groups 4 and 5 with sero-positive levels of anti-rabies antibodies will be determined prior to vaccination, and 28 days post Dose 3. Antibody levels after the third dose will also be investigated using reverse cumulative curves.

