10.5.1. Randomization Procedures

Eligible subjects will be randomized to their assigned group with secure IWRS (or in the absence of web connectivity, IVRS), which will be developed and managed by the PATH designated CRO. The IWRS/IVRS allows authorized staff from the study site to perform subject randomization and treatment assignment 24 hours a day, 7 days a week.

Subjects will be stratified by baseline parasitemia status and then block randomized. Among those positive for parasitemia at baseline a total of 363 will be randomized. The first 105 will be randomized in a 1:1:1 ratio with 35 subjects assigned to each of Groups 1, 3 and 4. The next 258 subjects with baseline parasitemia will be randomized in a 1:1 ratio to Groups 1 and 4 with a total of 129 additional subjects per group. Two hundred fifty-six subjects that are negative for parasitemia at baseline will be randomized with a 1:1 ratio to Groups 2 and 5. This randomization schedule will result in a total of 164, 128, 35, 164, and 128 for Groups 1 through 5, respectively. Additional details of the randomization procedure, such as block size, will be described in the Randomization Plan. HIV infection status will be noted prior to randomization, and individuals will be stratified across the groups to the extent possible. The proportion of subjects per group that are HIV positive will be capped near 20-25% for each group.

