14.1.3. Data Capture Methods (CRF Development and Completion)

Clinical data recorded in source documents, including the barcoded CRF pages, should be completed in a neat, legible manner to ensure accurate interpretation of data. Source documentation supporting the CRF data should document the dates and details of study procedures, AEs and subject status. The PI will ensure that all information in the CRFs and all other source documents that support the data collected from each subject are maintained in a secure area and treated as confidential material.

Data reported in the CRF that is derived from other source documents should be consistent. It is the PI's responsibility to ensure the accuracy, completeness, and timeliness of the data reported in the subject's CRF and any supporting documentation.

Clinical data entered in the barcoded CRFs and other source documents (as listed above) are uploaded to a 21 CFR Part 11 compliant EDC system using intelligent character recognition software. The scanned pages are then verified against data captured in the database by the data management staff at DFnet. For randomization, data confirming eligibility of the subject, *P.falciparum* infection status and HIV status at screening (based on source data as listed above), is entered directly into the same EDC system by site staff at Visit 2.

The database includes password protection and internal quality checks, such as automatic range checks, to identify data that appear inconsistent, incomplete, or inaccurate.

Additionally, a description of this clinical trial will be available on <http://www.ClinicalTrials.gov>, as required by U.S. Law. The clinicaltrials.gov registry will not identify any individual participants and will include a summary of the results.

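### HIV status is balanced at randomisation, but both efficacy Cox models name only group assignment; stratifying by HIV status is a small, free improvement

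*Protocol*

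**What the plan says.** **Analysis.** Section 10.4.2 states that VE against first PCR-positive infection in baseline-positive adults "will be assessed using Cox proportional hazards regression with a covariate for group assignment to compare Groups 1 and 4". Section 10.4.3 states that the secondary comparison "will be assessed using Cox proportional hazards regression with a covariate for group assignment to compare Groups 2 and 5". Both sections take the VE estimate (1 minus the hazard ratio), the 95% CI and the p-value from the model so named.

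**Randomisation.** Section 10.5.1 says "HIV infection status will be noted prior to randomization, and individuals will be stratified across the groups to the extent possible". Section 7.1.1 says "Subjects found to be HIV positive (stage 1 and 2) will be equally randomized among all study groups to the extent possible". Section 14.1.3 adds that, for randomisation, "infection status and HIV status at screening (based on source data as listed above), is entered directly into the same EDC system". On the expected share of HIV-positive subjects, section 5.3.2 reads "estimated to be approximately 15%. As such, we intend to cap HIV-positive enrollees at approximately 20-25" per cent.

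**Left to the SAP.** Section 10.1 lists among the SAP's contents "Specification of potential adjusted analyses and a statement with which covariates or factors will be included". The SAP is not at hand.

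Elsewhere in the statistical section, HIV status appears only as a baseline descriptive variable (10.4.6). Baseline parasitaemia, the other stratification factor, is constant within each comparison and needs no term.

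**The concern.** A factor used to balance the arms is normally carried into the analysis. When it is left out of a Cox model and is prognostic, two small things happen.

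- The group-only model estimates a marginal hazard ratio, which lies slightly closer to 1 than the ratio within HIV strata.
- Balancing the arms on HIV reduces the true sampling variation of the estimate, but the group-only model does not know this. Its standard error is slightly too large and the test mildly conservative.

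What is at stake is a little power and a slight understatement of the within-stratum VE. It matters somewhat more for Groups 2 v 5, which are planned at 80% power. Validity is not at stake.

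**Working it through.** **1. The plan's own figures.** Section 10.5 gives HR 0.5, one-sided alpha 0.025, 10% dropout and a 40% attack rate over 6 months. Table 9 gives 164 per group, 92 events and 90% power (primary), and 128 per group, 72 events and 80% power (secondary).

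- Expected 6-month risk: control 0.40; vaccine 1 − 0.6^0.5 = 0.2254; mean 0.3127.
- Expected events: 2 × 164 × 0.9 × 0.3127 = 92.3, and 2 × 128 × 0.9 × 0.3127 = 72.0. Both match Table 9.
- Power, Schoenfeld form, Φ(√d × |ln 0.5|/2 − 1.96): 91.4% at 92 events, 83.7% at 72.
- Power, Freedman form, Φ(√d × (1 − 0.5)/(1 + 0.5) − 1.96): 89.2% and 80.7%.

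Table 9 is therefore sound, and the point below does not alter it.

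**2. The two models.** With x for group and h for HIV status, VE = 1 − exp(β) in both:

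- group-only: λ(t | x) = λ0(t) exp(βx)
- stratified: λ(t | x, h) = λ0h(t) exp(βx), with a separate baseline hazard for each HIV stratum

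**3. Simulation set-up** (40,000 trials per scenario).

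- 147 per arm (90% of 164) and 115 per arm (90% of 128).
- HIV share 15% (expected) or 25% (upper end of the cap), exactly balanced between arms.
- Control attack rate held at 40% over 6 months across the HIV mix; within-stratum HR 0.5, or 1.0 under the null.
- Uniform entry over 6 months. PCR detection at day 225 and then every 21 days, to day 372 (Epoch 2) or 540 (Epoch 3).
- Everyone completes Epoch 2; Epoch 3 stops at 92 or 72 events (mean events 98 and 77).
- Efron ties, one-sided 0.025. Monte Carlo error is 0.13 to 0.2 points for power and about 0.08 points for type I error.
- The HIV hazard ratio for infection is an assumption, because the protocol gives none.

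**4. Results.** Ranges cover both HIV shares; the VE, SE and type I columns also cover both comparisons.

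| HIV hazard ratio | VE, stratified minus group-only (points) | Power 1 v 4, group-only / stratified (%) | Power 2 v 5, group-only / stratified (%) | Null: group-only model SE above sampling SD (%) | Null: group-only one-sided type I (%) |
|---|---|---|---|---|---|
| 1.5 | 0.1–0.2 | 91.7–91.9 / 91.9 | 84.1–84.2 / 84.3 | 0.1–0.5 | 2.3–2.4 |
| 2 | 0.6–0.7 | 91.4–91.6 / 91.9–92.2 | 83.2–83.3 / 84.0–84.2 | 0.9–2.1 | 2.1–2.4 |
| 3 | 1.6–2.1 | 89.9–90.4 / 92.1 | 81.0–81.8 / 84.0–84.4 | 3.9–5.6 | 1.8–2.0 |

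- For a protective association, the VE difference is 0.3 to 0.4 points at hazard ratio 0.5 and 0.5 to 1.0 at 0.33.
- Stratified type I error is 2.3 to 2.5%.
- If HIV is not prognostic (hazard ratio 1), stratifying costs at most 0.1 point of power.
- One case in full, Groups 1 v 4 with 25% HIV and hazard ratio 2: VE 49.6 v 50.3%, power 91.6 v 92.2%, type I error 2.19 v 2.43% (group-only v stratified).

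**5. Scale.** Stratifying does not shrink the SE of the log hazard ratio (for example 0.2114 group-only v 0.2120 stratified). With SE 0.2114, the expected 95% CI for VE in Groups 1 v 4 is 1 − exp(ln 0.5 ± 1.96 × 0.2114), about 24 to 67%. A VE shift of at most 2.1 points is small beside that.

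**6. Check by a simpler simulation** (2,500 trials per scenario, exponential times without the visit schedule; Monte Carlo error 0.6 to 0.8 points for power).

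- HIV hazard ratio 3, group-only v stratified power: 89.5–89.8 v 90.2–92.1% (Groups 1 v 4) and 79.7–80.2 v 81.9–83.3% (Groups 2 v 5).
- Mean estimated HR in the same scenarios: 0.512–0.516 group-only v 0.496–0.501 stratified, against a true 0.50.
- Null, Groups 1 v 4, 25% HIV, hazard ratio 3: group-only model SE 0.185 against a sampling SD of 0.172.
- At hazard ratios 1 to 2, most differences are under 1 point and cannot be told from zero at this size.

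The direction and rough size agree with the larger run.

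**The case against.** **Adjusted analyses belong to the SAP, which may already include HIV.** This stands in part. But section 10.1 defers potential adjusted analyses, whereas 10.4.2 and 10.4.3 name the main model and tie the estimate, CI and p-value to it. A SAP that put HIV in the main model would go beyond that text.

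**Nothing is wrong with the named model, and the gain rests on an assumed HIV effect.** Both are true. The group-only test is valid, and only a hazard ratio near 3 yields 2 to 3 points of power. Enrolled HIV-positive subjects are clinical stage 1 or 2 and judged healthy, and nothing in the protocol supports so large an effect. This is why the point is an improvement and not an error.

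**Stratifying changes the estimand** from a marginal to a within-stratum hazard ratio. True; the shift is 0.1 to 2.1 VE points over the range examined.

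**Exact HIV balance was simulated, while the protocol promises it only as far as possible.** This is a fair limit on the SE and type I figures. With simple randomisation in the smaller simulation (Groups 1 v 4, 25% HIV, hazard ratio 3), the SE excess disappeared: model SE 0.1852 against a sampling SD of 0.1881 under the null. The power gain did not: 87.5% group-only v 91.0% stratified.

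**A protocol amendment is not costless.** Section 13.2.2 requires ethics approvals even for administrative amendments. That is a procedural cost; there is no statistical one beyond 0.1 point of power.

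**Conclusion.** The point holds as a free improvement. HIV status is used to balance the groups, yet the two models that supply the efficacy results name only group assignment. The current analysis remains valid and, if HIV is prognostic, is slightly conservative.

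Stratifying gains almost nothing at an HIV hazard ratio of 1.5, roughly 0.5 to 1 point of power at 2, and roughly 2 to 3 points at 3, with the larger gains in Groups 2 v 5. These figures rest on assumed HIV effects, an HIV share of 15% or 25%, a within-stratum VE of 50%, and close HIV balance between arms.

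**What to change.** In 10.4.2 and 10.4.3, state that the Cox model is stratified by HIV status as recorded for randomisation, and keep the group-only model as a sensitivity analysis. Entering HIV status as a covariate is a standard alternative, but one form should be named in advance; the figures above are for the stratified form.

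The cost is one clause in each section, with the approvals in 13.2.2. HIV status is already collected, and sample sizes and the 92 and 72 event targets stay as they are. The SAP should match, and the choice should be fixed before database lock, because the trial is open label and a covariate chosen later would be open to challenge.

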10.4.3. Analysis of the Secondary Endpoint(s)

Efficacy:

Vaccine efficacy against the first PCR-positive *P. falciparum* infection among adults who were *P. falciparum* negative at baseline will be assessed using Cox proportional hazards regression with a covariate for group assignment to compare Groups 2 and 5. The vaccine efficacy estimates (1-hazard ratio), 95% CI, and p-values will be calculated from this model. Cumulative incidence graphs will also be provided. This analysis will be conducted in the ATP for efficacy cohort.

Immunogenicity:

The primary analysis will be based on the ATP for immunogenicity cohort for analysis of immunogenicity. A secondary analysis based on the TVC will be performed to complement the ATP analysis.

Anti-CS antibodies:

The percentage of subjects with sero-positive levels of anti-CS (proportion of subjects with anti-CS antibody levels with 95% CI) will be determined as shown in Appendix F. Antibody levels after the third dose will also be investigated using reverse cumulative curves.

Anti-HBs antibodies:

The percentage of subjects with sero-positive levels of anti-HBs (proportion of subjects with anti-HBs antibody levels greater than the lower limit of detection/assay dependent) will be determined prior to vaccination, and 14 days post Dose 3. Antibody levels after the third dose will also be investigated using reverse cumulative curves.

Anti-rabies antibodies:

The percentage of subjects in Groups 4 and 5 with sero-positive levels of anti-rabies antibodies will be determined prior to vaccination, and 28 days post Dose 3. Antibody levels after the third dose will also be investigated using reverse cumulative curves.

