4.2.2. Secondary Endpoints

Secondary endpoint for vaccine efficacy:

The secondary endpoint is defined as the time to first PCR-positive malaria infection in Groups 2 and 5 during the ADI phase of the study. Vaccine efficacy in African adults administered RTS,S, and who are negative for *P. falciparum* infection at baseline and given anti-malaria chemoprophylaxis (Group 2) are compared to rabies vaccinated adult subjects who are negative for *P. falciparum* infection at baseline and given anti-malaria chemoprophylaxis (Group 5).

Secondary endpoint for safety:

- Frequency count and proportion of subjects reporting serious adverse events (SAEs) during the whole study period
- Frequency count and proportion of subjects reporting solicited local and systemic adverse events within 7 days after each vaccination
- Frequency count and proportion of subjects reporting unsolicited adverse events within 28 days after each vaccination

Secondary endpoint for immunogenicity:

- Anti-circumsporozoite (CS) antibody levels & avidity at time points shown in Appendix F.
- Hepatitis B surface antibody (HBsAb) levels at time points shown in Appendix F.

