5.2. Participant Exclusion Criteria

An individual who meets any of the following criteria will be excluded from participation in this study:

- Planned administration/administration of a vaccine not foreseen by the study protocol from within 30 days before the first dose of study vaccine until 30 days after the last dose of study vaccine.†

† In the context of the COVID-19 pandemic, the administration of the COVID-19 vaccine will be allowed as an exception to this exclusion criteria as follows. The study team will work with the participant to attempt to have any COVID-19 vaccine administration occur 30 days or more before or after study vaccinations. When this is not possible, COVID-19 vaccination will be allowed 10 days or more before or after study vaccination. Intervals shorter than 10 days can be allowed on a case-by-case basis in discussion with the sponsor.
- Any prior receipt of any rabies vaccine or experimental malaria vaccine.
- Confirmed or suspected significant immunosuppressive or immunodeficient condition as determined by the investigator, including clinical stage 3 or 4 human immunodeficiency virus (HIV) infection (Appendix H).
- A family history of congenital or hereditary immunodeficiency.

- History of allergic reactions, significant IgE-mediated events or anaphylaxis to previous immunizations.
- History of any neurologic disorders.
- Acute disease (defined as the presence of a moderate or severe illness with or without fever), including acute malaria, at the time of enrolment. All vaccines can be administered to persons with a minor illness, such as diarrhea or mild upper respiratory infection without fever, i.e. temperature $< 37.5^{\circ}\text{C}$ *. Individuals excluded with acute disease, including acute malaria, can become eligible again after complete recovery of the illness, including appropriate treatment as applicable, and can be rescreened at a later date.

* Temperature readings may be taken by site staff either using either oral, axillary, or infrared thermal thermometers during clinic or field visits, while subjects enrolled in the reactogenicity cohort will be supplied with oral thermometers for the purposes of recording their own temperature measurements in the memory aid over 7 days after each vaccination.

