10.3.5. ATP cohort for immunogenicity

The ATP cohort for immunogenicity will include all subjects included in the TVC who received all vaccinations according to protocol procedures and within the protocol specified intervals, performed blood samplings for immunogenicity according to protocol intervals, and did not use any medication or blood products forbidden by the protocol and did not have any reported underlying medical condition influencing immune responses.

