APPENDIX F. BIOLOGICAL SAMPLES FOR IMMUNOGENICITY TESTING

SAMPLES COLLECTED	Visit #	2	5	6	7	11	13	17	20	27	Study Termination Visit
		-									
	Study day	27	1	2	8	29	57	197	225	372	TBD*
Secondary endpoint -Groups 1, 2, 3											
Serum	anti-CS NANP levels	●	●			●	●	●	●	●	●
	anti-CS NANP avidity	●	●			●	●	●	●	●	●
	anti-CS C-term levels	●	●			●	●	●	●	●	●
	anti-CS C-term avidity	●	●			●	●	●	●	●	●
	anti-HbsAb antibodies	●	●			●			●		
Exploratory											
Serum	Anti-rabies antibodies -(first 50 subjects in Group 4 and Group 5)		●						●		
PBMC	Flow cytometry from all RTS,S vaccinated subjects (Gps 1,2,3)	●	●		●				●		
Transcriptomics	Transcriptomics Groups 1, 2, 3, 4, 5	●	●	●	●				●		

* Study Day for the Study Termination Visit will be the day according to the criteria as specified in section 7.1.1, part E of the protocol being met.

**APPENDIX G. ADULT NORMAL REFERENCE VALUES – KEMRI &
USAMRD-A KISUMU CLINICAL LABORATORIES**

Analyte	Adult Male	Adult Female	Unit	Critical Values	
				Low	High
Creatinine	54.2 - 137.8	52.4 - 96.8	µmol/L	N/A	Male:>248; Female:>174.2
ALT	12.0 - 80.6	10.7 - 61.3	U/L	N/A	Male:>201.5; Female:>153.3
WBC	3.3 - 9.6	3.7 - 9.1	$\times 10^3/\mu\text{L}$	< 2.0	≥ 40.0
HGB	12.6 - 17.2	9.0 - 14.9	g/dL	Male: <8.0; Female: <7.0	>20.0
Platelets	126 - 356	147 - 454	$\times 10^3/\mu\text{L}$	<80	>1000

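### Anti-HBs percent positive and curves after Dose 3 pool subjects with and without prior hepatitis B antibody, which attenuates group differences; splitting by day 1 status uses samples already planned

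*Protocol*

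**What the plan says.** Section 4.2.2 of the protocol names the secondary endpoint as "Hepatitis B surface antibody (HBsAb) levels at time points shown in Appendix F". Section 10.4.3 turns it into two summaries. One is numerical: "The percentage of subjects with sero-positive levels of anti-HBs (proportion of subjects with anti-HBs antibody levels greater than the lower limit of detection/assay dependent"); this "will be determined prior to vaccination, and 14 days post Dose 3". The other is graphical: "Antibody levels after the third dose will also be investigated using reverse cumulative curves". Neither is described as depending on, or being split by, the subject's status before Dose 1.

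The only prior-vaccine exclusion in section 5.2 is "Any prior receipt of any rabies vaccine or experimental malaria vaccine". Hepatitis B vaccination, past infection and existing antibody do not appear in sections 5.1 or 5.2, and the screening tests in Appendix A include no hepatitis B marker. The ATP cohort for immunogenicity (section 10.3.5) requires that subjects "did not have any reported underlying medical condition influencing immune responses", which does not address prior hepatitis B immunity.

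In Appendix F, the row labelled "anti-HbsAb antibodies" for Groups 1, 2 and 3 is marked at study days -27, 1, 29 and 225. Dose 3 is on day 197 (Appendix B).

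**The concern.** RTS,S carries hepatitis B surface antigen, so anti-HBs is a second antibody response to the same vaccine. The trial asks whether *P. falciparum* infection blunts the vaccine response and whether clearing it restores the response. Group 3 (35 infected, untreated subjects) is included for immunology alone, as the reference for a blunted response.

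A detection-limit cutoff answers whether antibody is present. In an adult who already had antibody, presence after Dose 3 says almost nothing about the vaccine. Such subjects enter the post-Dose-3 percentage as positives in every group and pull the groups together. The reverse cumulative curves pool the same subjects, so a curve mixes primary responses with pre-existing or boosted antibody. Groups 1 and 2 come from different parasitemia strata (section 10.5.1) and are not randomised against each other, so their baseline anti-HBs need not be similar.

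**Working it through.** The protocol states no expected anti-HBs rate, baseline prevalence, hypothesis or power, so there is no planned figure to reproduce. All rates below are assumptions.

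**Inputs**
- b: fraction above the detection limit before Dose 1. Not in the protocol; range shown 0 to 50%.
- r: fraction of baseline-negative subjects who are positive after Dose 3. Not in the protocol; assumed 95% (Group 1) v 75% (Group 3), with 90% v 60% and 99% v 95% as alternatives.
- Group sizes 164 and 35 (Table 1), with 90% evaluable (section 7.1.1): 0.9 × 164 = 147.6, taken as 148; 0.9 × 35 = 31.5, taken as 32.

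**Step 1: percent positive after Dose 3.** If baseline positives stay above the limit, the observed percentage is b + (1 − b)r. With no vaccine effect (r = 0) it equals b. With the same b in both groups, the difference is (1 − b)(r₁ − r₃).

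| b | Group 1 (r = 95%) | Group 3 (r = 75%) | Difference, points | Difference if 90% v 60% |
|---|---|---|---|---|
| 0% | 95.0 | 75.0 | 20 | 30 |
| 10% | 95.5 | 77.5 | 18 | 27 |
| 20% | 96.0 | 80.0 | 16 | 24 |
| 30% | 96.5 | 82.5 | 14 | 21 |
| 40% | 97.0 | 85.0 | 12 | 18 |
| 50% | 97.5 | 87.5 | 10 | 15 |

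At 99% v 95%, the 4-point difference falls to 2 points at b = 50%.

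**Step 2: can the planned output undo this?** The pre-vaccination percentage estimates b, so r = (observed − b)/(1 − b). At b = 30%: (96.5 − 30)/70 = 95% and (82.5 − 30)/70 = 75%. The group rates come back exactly, provided nobody reverts to negative and the same subjects supply both samples. No confidence interval for r is planned.

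**Step 3: unequal baselines.** If r is the same in two groups but b differs, the difference in percent positive is (b₁ − b₂)(1 − r). A 10-point baseline imbalance gives 10 × 0.25 = 2.5 points at r = 75% and 10 × 0.05 = 0.5 points at r = 95%.

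**Step 4: power, Group 1 v Group 3, two-sided 0.05, 95% v 75%.**

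| b | All subjects | Baseline-negative only |
|---|---|---|
| 0% | 88.2% | 88.2% |
| 10% | 84.9% | 85.4% |
| 20% | 80.9% | 82.0% |
| 30% | 76.3% | 77.9% |
| 50% | 64.8% | 67.0% |

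The largest gain is 67.0 − 64.8 = 2.2 points. At 99% v 95% there is none (29.5% either way at b = 50%).

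**Step 5: time point.** Day 225 − day 197 = 28 days. Fourteen days after Dose 3 is day 211 (Visit 19), a field visit at which Appendix C schedules no serum and Appendix F no anti-HBs. The 14-day figure in section 10.4.3 therefore has no matching sample.

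**The case against.** The strongest reply is that nothing in the definition is false. It is called sero-positivity, not seroconversion or vaccine response, and a cutoff measures exactly that. The pre-vaccination percentage stands beside it, and step 2 shows that group-level seroconversion can be recovered from the two. Antibody levels are the named endpoint and get their own curves, where a weak responder with prior antibody can still show a low level. No between-group anti-HBs test is planned, and section 10.1 leaves detailed methods and adjusted analyses to the SAP, which is not at hand.

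Most of this stands and sets the size of the point. A reader might infer that prior antibody hides the hypo-responsiveness under study. The documents do not support that: the pre-vaccination percentage and the levels are reported, anti-CS levels and avidity and the cellular assays do not use this cutoff, and the baseline prevalence is unknown and could be low. A reader might also infer that a baseline imbalance between Groups 1 and 2 passes in full into the percent-positive contrast; step 3 shows that only the fraction 1 − r does.

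Two things survive. The protocol does fix the summary, as a cutoff pooled over baseline status, so this is a stated choice and not a detail left open. And back-calculation from two percentages is not a planned estimate: it needs the no-reversion condition, comes with no interval, and does nothing for the pooled curves.

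**Conclusion.** The point holds as an attenuation in one secondary immunogenicity summary. Differences in percent positive are multiplied by (1 − b) when b is equal across groups and baseline positives stay positive: 20 points become 18 to 10 for b from 10 to 50%, and the effect vanishes as b approaches zero. Both b and the response rates are assumptions. The post-Dose-3 curves pool the same subjects; the documents give no basis for sizing that effect.

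The gain from a change is an estimate that measures response to the vaccine, not power. Vaccine efficacy, anti-CS and the cellular readouts are untouched. It is worth changing because it is cheap. The mismatch between 14 days in section 10.4.3 and day 225 in Appendix F is separate and does not depend on any assumption.

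**What to change.** In section 10.4.3, carried into the SAP:

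- Classify subjects in Groups 1, 2 and 3 by the day 1 anti-HBs result.
- Among those below the cutoff on day 1, report the percentage above it after Dose 3, by group, with 95% CI.
- Among those above it on day 1, report the fold-rise from day 1.
- Draw the reverse cumulative curves separately by day 1 status.
- Adjust any between-group comparison of levels for day 1 log anti-HBs.
- Reconcile the stated 14 days after Dose 3 with the Appendix F sample on day 225.

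The overall percentages before and after vaccination can stay as a descriptive table.

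**Cost.** Wording only: anti-HBs is already scheduled on days -27 and 1, so no visit, sample or assay is added. The seroconversion denominator shrinks, most noticeably in Group 3, where 20% baseline positivity would leave 0.8 × 35 = 28 subjects before dropout. Little or no power is gained in return.
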